Since the introduction of our standardized approach, we have improved antibiotic tailoring by developing methods of increasing detection of anaerobic species through our use of bile aspirate in addition to collection of bile swabs³⁸. However, similar to other institutions, it takes an average of 4 days for final bacterial culture results to be generated⁴⁴, and the majority of cultured microbial species have been found to exhibit multi-resistance phenotypes. This means that for the first 4-days post-surgery many of our patients at risk of developing SSI are receiving suboptimal antimicrobial therapy. This provides potential pathogens a window of opportunity to grow and propagate prior to introduction of tailored antimicrobial therapy. Rapid methods of detecting microbial species and antimicrobial resistance phenotypes are required to shorten this window of opportunity. Our data shows that in patients with positive bile cultures it took an average of 7 days to complete microbial identification and AST for bacterial and fungal species (range = 3 – 24 days), and it took 24 days to confirm the absence of biliary microbes (5 days for aerobic cultures, 14 days for anaerobic cultures, 24 days for fungal cultures). In particular, delays in detecting *Candida* species, was of concern due to the increased risk of SSI in patients with biliary candidiasis⁴⁵. In our own patient cohort, 17% of patients were positive for biliary candidiasis, and the microbe was the presumptive cause of 22% of SSIs. In patients with biliary candidiasis, it took an average length of 4.6 days for fungal identification, and an additional 6 days for anti-fungal susceptibility testing to be complete. As anti-fungals are not part of the recommended perioperative prophylactic antimicrobial treatment course, it meant that during the first 2 weeks post-surgery these patients were at increased risk of SSI due to untreated biliary candidiasis.

A single diagnostic test that would enable simultaneous identification of bacterial species (aerobic, anaerobic, fastidious), fungal species, and antimicrobial resistance in an expedited

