fashion would be highly advantageous. It would allow for all the microbial information to be generated in a single report, enabling the administration of optimal tailored antibiotics in the early postoperative window without the need for continuous changes to the treatment regimen as new information becomes available. It would also enable early cessation of antimicrobial prophylaxis if no microbes are detected, potentially reducing the complications associated with use of broad-spectrum antibiotics.

We hypothesized that use of metagenomic Oxford Nanopore (ONT) sequencing, a real-time method of sequencing that has been demonstrated to detect microbial species in as little as 6 hours^{42,46,47}, could be developed as a tool for rapid detection and characterization of biliary microbes. We have since developed methods of detecting intraoperative bile microbes, and have recently published the promising results of a prospective clinical trial that was performed to determine the feasibility and utility of ONT sequencing in detection of microbial species and antibiotic resistance genes using intra-operative bile from patients undergoing pancreatic head resection^{44,48}. Our preliminary data would suggest that not only is this technique feasible, but our ONT sequencing results highly correlate with traditional culture microbial identification and does so with a median time of 14 hours compared to 98 hours for traditional culture, a turnaround time improvement of 92%. Furthermore, the results of our study found that when standard cultures (SC) were negative (i.e. no further antibiotic therapy needed) the ONT perfectly correlated. This suggested that ONT could be used to identify patients with negative biliary microbes, enabling a more rapid cessation of unnecessary antimicrobial therapy in patients. This would improve antibiotic stewardship, a continual goal in surgical patient care.

Given these promising preliminary results, we aim to reduce the rate of SSI while minimizing overutilization of antibiotic therapy in patients undergoing pancreatic head resection by providing supplemental ONT data in addition to standard clinical cultures. This will provide not only an important potential diagnostic, but will also elucidate microbial communities within contaminated bile, potentially leading to improved targeted approaches in the future.

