Pancreaticoduodenectomy, % (n)	79 (33)	42.9 (18)	35.7 (15)	
Biliary instrumentation, % (n)	52 (22)	52.4 (22)	0 (0)	<0.0001
Vascular reconstruction, % (n)	38 (16)	31.0 (13)	7.1 (3)	0.0079

BMI, body mass index; IQR, interquartile range

Comparison of our optimized ONT sequencing protocol SC results revealed that our ONT protocol had identified 100% of biliary microbial contamination cases, detected 75% of cultured bacterial species and 76% of cultured fungal species, and predicted 81% of antibiotic resistance phenotypes observed using SC results ^{44,48}. With regards to detection of common biliary pathogens ^{3,54-57}, our ONT protocol improved detection of biliary candidiasis, detected 100% of cases of biliary *Escherichia coli* and biliary *Klebsiella*, and detected 83% of biliary *Enterobacter*, 76.5% of biliary *Enterococcus*, 93.8% of biliary *Streptococcus*. However, ONT did not detect one case of *Pseudomonas* infection and one case of *Staphylococcus aureus*, indicating as proposed in this study that SC techniques should be run alongside ONT protocols to ensure that no microbial species are missed. As for detection of pathogens of high clinical concern (i.e. ESBL, CRE species), ONT similar detection rates compared to SC, and potentially improved detection of *E. coli*, *K. oxytoca*, *K. pneumoniae*, and *Citrobacter freundii*. Overall, ONT improved detection of microbial species (particularly with regards to anaerobic species and fungal species) and predicted a significantly higher number of antibiotic resistance phenotypes than were identified using SC. Significantly, the results turnaround for ONT sequencing was just 14 hours compared to an average turnaround time of 98 hours for SC. On average, it took 4.8 days (range = 1 – 15 days) to complete microbial identification and an additional 2 days (range = 0 – 9 days) to complete AST for the culture positive samples. Delays greater than 5 days in completing microbial identification occurred in samples with multiple aerobic species of the same genus (*Enterococcus* spp., *Klebsiella* spp., *Streptococcus* spp.), anaerobic species (*Schaalia (Actinomyces) turicensis*, *Finegoldia magna*, *Veillonella* sp., *Actinomyces johnsonii*, *Parvimonas micra*), and/ or fungal species *Saccharomyces cerevisiae*, *Candida* spp.), and on average, optimal antimicrobial therapy was delayed for 7 days. Use of a test that would enable microbial identification and prediction of AMR phenotypes within 24hrs post-surgery, would, therefore, have significantly shortened the delay in patients receiving optimized tailored antimicrobial therapy post-surgery.

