2.3 Secondary Study Endpoints

- Cost effectiveness (reduced total hospital costs)
- Timeliness of sample analysis
- Reduction in SSI

3 Subject Selection, Enrollment and Withdrawal

Any adult, male or female, over age 18, undergoing pancreaticoduodenectomy or total pancreatectomy for benign or malignant indication.

Target accrual: 140 patients.

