6.2 Statistical Methods

Descriptive Statistics

The primary analysis of this study will be a modified intention to treat analysis (ITT), performed to determine how use of ONT changed patient treatment, i.e. did use of ONT improve antibiotic stewardship. Proportions of patients with detection of microbes of interest will be estimated along with exact 95% binomial confidence intervals. Comparisons of the proportions between the two study arms will be compared using Fisher's exact test or Chi-square test as appropriate. We will calculate the time from randomization to first microbial detection within a patient. We will report the mean difference in time to first microbial detection within 96 hours post randomization in both treatment arms, together with a 95% confidence interval. Comparison of time to first microbial detection within 96 hours post randomization, will be performed using Wilcoxon rank sum test or two sample t-test as appropriate. If there are any baseline imbalances in demographic or clinical variables between the two groups, we will perform the analysis using univariable and multivariable linear regression adjusting for these variables with imbalances as possible confounders. Duration of antibiotics, total number of different antibiotics, and broad-spectrum antibiotics vs narrow-spectrum antibiotics administered in the two arms will be compared to determine if use of ONT improved antibiotic stewardship by significantly reducing the duration of perioperative antibiotics and use of broad-spectrum antibiotics

Secondary analysis will evaluate SSI's will be evaluated and classified using ACS NSQIP definitions and data collected will include mortality rate, SSI incidence rate, ICU length of stay, total length of hospital stay, need for interventional procedures, and hospital readmission. Statistical analysis will be performed by the study team to determine if use of ONT significantly improved patient outcome compared to patients who received standard of care

only. The secondary endpoint of the study is a binary endpoint i.e. whether patients develop SSI (yes, no). Association between the secondary outcome and predictor variables will be assessed using univariable and multivariable logistic regression.

In both primary and secondary analysis, the following variables will be assessed for inclusion in the regression models

- Age at time of surgery DOB
- BMI at time of surgery RAVE calculate
- Sex

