- 77. Sanderson, N. D. *et al.* Real-time analysis of nanopore-based metagenomic sequencing from infected orthopaedic devices 06 Biological Sciences 0604 Genetics 06 Biological Sciences 0605 Microbiology. *BMC Genomics* **19**, 1–11 (2018).
- 78. Miller, S. *et al.* Laboratory validation of a clinical metagenomic sequencing assay for pathogen detection in cerebrospinal fluid. *Genome Res.* **29**, 831–842 (2019).

14 Supplementary Materials

S1. Standard cultures performed on the bile samples

Swab samples were inoculated into thioglycolate broth (thio), chocolate blood agar (CBA), tryptic soy agar with 5% sheep blood (BAP), eosin-methylene blue agar and Columbia CNA agar with 5% sheep blood, colistin and nalidixic acid (CNA). Bile fluid aspirate samples were aseptically removed from the transport vial and one aliquot of fluid placed onto each of chocolate blood agar, BAP, eosin-methylene blue agar, and CNA culture media for aerobic culture. Aerobic culture plates were incubated at 35°C in 5% CO₂ and examined daily for growth for up to 5 days. Anaerobic culture media were inoculated in parallel and included CDC anaerobe 5% sheep blood, phenylethyl alcohol blood agar, laked Brucella blood agar with kanamycin and vancomycin and a BAP used as an aerotolerance screen.

S2: Protocol for the identification of aerobic cultures

PROCEDURE:

1. Culture reading schedule:
 - a. Based on the time the culture was set up, read cultures in two batches beginning at 8:00 a.m. and 12:30 p.m. to allow for a minimum incubation time of 16 hours. At 8:00 a.m. move plates cultured by the midnight tech (found on the bottom shelf of the incubator) to the appropriate a.m. shelf to complete their incubation. Culture set up Initial examination 8:00 a.m. - 4:00 p.m. 4:00 p.m. – Midnight, Midnight- 8:00 a.m. 8:00 a.m., the next day 12:30 p.m., the next day 8:00 a.m., the next day
 - b. The schedule for reading urine cultures is found in Urine Culture [011327].
 - c. The schedule for reading stool cultures is found in Stool Culture [011342].
2. Initial examination of GEN and GENS cultures: Open the DGEN1 work list. Sort the work list by last name to separate bench I and bench II orders.
 - a. Separate all positive cultures from the negative cultures.

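### The only planned time analysis stops at an undefined first microbial detection, which culture can reach before identification and susceptibility are complete, so it can understate the speed difference the trial is about

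*Combined protocol and SAP*

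**What the plan says.** Section 2.3 (Secondary Study Endpoints) lists "Timeliness of sample analysis" and gives no start, stop or milestone. Section 6.2 supplies the only time analysis: "We will calculate the time from randomization to first microbial detection within a patient", followed by "We will report the mean difference in time to first microbial detection within 96 hours post randomization in both treatment arms", tested by Wilcoxon or t-test. It does not say whether detection means visible growth, a named species or a posted report. It specifies no analysis of time to complete identification, to a susceptibility or resistance result, to a negative result, or to a change of therapy.

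The speed rationale uses other milestones. Section 1.1 says ONT agrees closely with culture and "does so with a median time of 14 hours compared to 98 hours for traditional culture, a turnaround time improvement of 92" per cent. Section 1.4 says "the results turnaround for ONT sequencing was just 14 hours compared to an average turnaround time of 98 hours for SC". Section 1.1 also says "it takes an average of 4 days for final bacterial culture results to be generated". For culture-positive samples, Section 1.4 reports that "it took 4.8 days (range = 1 – 15 days) to complete microbial identification and an additional 2 days (range = 0 – 9 days) to complete AST". Section 1.1 elsewhere puts identification plus AST, bacterial and fungal, at 7 days on average.

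On laboratory practice, Supplementary Materials S2 tells staff to "read cultures in two batches beginning at 8:00 a.m. and 12:30 p.m. to allow for a minimum incubation time of 16 hours". S4 places the primary examination of anaerobic plates at 48 hours.

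**The concern.** The hypothesis in Sections 2.1 and 6.2 is that faster identification lets patients receive tailored antibiotics sooner. Tailoring draws on which organisms are present and what they resist. An ONT report delivers species and predicted resistance together (Section 2.1, General Design), whereas culture delivers them in stages. Sections 1.1 and 1.4 attribute culture delay to mixed growth, anaerobes, yeasts and AST, much of which comes after the first organism appears.

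An event defined by the first microbe may therefore set a whole ONT report against the first partial sign from culture. Consider a patient with an aerobe visible on the first plates and a yeast identified at the 4.6-day average of Section 1.1 (4.6 × 24 = 110 h). That patient could be scored as detected on day 1. At stake is whether the timeliness endpoint can answer the question in the trial's title.

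**Working it through.** **The protocol's own speed figure.** (98 − 14)/98 = 85.7%, not the stated 92%. With 7 days (168 h) in place of 98 h, (168 − 14)/168 = 91.7%. So 92% fits the identification-plus-AST time better than the 98 h printed beside it. Since 98/24 = 4.1 days, 98 h matches the 4 days given for final bacterial results. The documents do not state exactly where the 98 h ends.

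**First aerobic reading (S2 schedule).**
- Set-up 8 a.m. to 4 p.m., read 8 a.m. next day: 16 to 24 h.
- Set-up midnight to 8 a.m., read 8 a.m. next day: 24 to 32 h.
- Set-up 4 p.m. to midnight, read 12:30 p.m. next day: this computes to 12.5 to 20.5 h, which conflicts with the 16 h minimum. The schedule is broken in the extracted text, so this slot is not used.

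**Gap by milestone.** Gap = culture time − 14 h. Share = gap/84, where 84 = 98 − 14.

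| Culture milestone | Culture time (h) | Gap (h) | Share of 84 h |
|---|---|---|---|
| First aerobic reading, daytime set-up | 16–24 | 2–10 | 2–12% |
| First aerobic reading, midnight to 8 a.m. set-up | 24–32 | 10–18 | 12–21% |
| First anaerobic plate examination (S4) | 48 | 34 | 40% |
| Quoted turnaround (1.1, 1.4) | 98 | 84 | 100% |
| Complete identification (1.4) | 4.8 × 24 = 115.2 | 101.2 | – |
| Identification plus AST (1.4) | (4.8 + 2) × 24 = 163.2 | 149.2 | – |
| Identification plus AST (1.1) | 7 × 24 = 168 | 154 | – |

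**If ONT also counts at its first detection.** Section 1.1 cites 6 h as the fastest. Taking 6 h for this trial is an assumption. The aerobic gap is then 16 − 6 = 10 h to 32 − 6 = 26 h, or 12 to 31% of 84 h.

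**The window.** The later culture averages (98, 115, 163 and 168 h) all exceed 96 h. Changing the milestone without changing the window would not work.

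**Negatives.** At the positivity rates in Section 6.1 (54% and 77%), 46% of culture results and 23% of ONT results have no detection time. Yet a negative ONT result leads to a treatment decision under Table 5.

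**Limits of these figures.** The first-reading times run from plate set-up and assume growth is visible and logged then. The planned measure runs from randomization, and the start of the 14 h clock is not given. The later figures are averages, while Section 1.1 calls 14 h a median. No standard deviation is given, so power cannot be computed for any of these measures.

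**The case against.** The strongest reply is that detection is undefined rather than wrongly chosen. The protocol often uses the word for species-level results. If it means a reported species, culture's time falls after the S2 work-up and the gap widens. This stands, and the missing definition is part of the defect. Even so, one reported species is still not the full organism list or a resistance result.

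A reader might infer that the 98 h figure already includes susceptibility. The documents do not support this: they tie about 4 days to final bacterial results and put identification plus AST at 6.8 to 7 days.

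A reader might also infer that the first-detection gap is only 2 to 10 h. That covers daytime aerobic set-up alone, with growth logged at first reading. Other set-up times, anaerobes and yeasts come later. The pilot isolate percentages show what grew, not when.

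It is tempting, too, to say that the trial cannot link test speed to treatment. That goes too far. Section 6.2 compares antibiotic duration, number and spectrum directly, and Section 5.3 captures and compares all culture and ONT results. First culture growth also matters in itself, because a positive culture affects management under Section 2.1.

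Finally, any understatement works against the sponsor's hypothesis, so it would not create a false claim of speed. This is correct and limits the seriousness of the point.

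**Conclusion.** The concern holds in a limited form. The sole time analysis ends at an undefined first detection within 96 h, and culture can reach that event while other species and AST are outstanding. It can therefore understate the difference in time to the results used for tailoring.

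For organisms visible on the first aerobic plates, the measurable gap is about 2 to 18 h with ONT at 14 h, or 10 to 26 h on the 6 h assumption. The gaps to later culture results are 84 h, 101 h, and 149 to 154 h. The small figures depend on growth being logged at the first reading and do not apply to anaerobes or yeasts. How many trial patients would fall in this group cannot be read from the documents.

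This is a secondary endpoint and the antibiotic comparisons are unaffected. It is still worth correcting, because speed is the trial's stated rationale.

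**What to change.** In Sections 2.3 and 6.2:

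- Define timeliness as hours from bile collection to (a) the last reported organism identification and (b) the last reported susceptibility or predicted-resistance result. Take both from medical-record posting times, using the ONT report in Arm 2 and the culture report in Arm 1.
- Replace the 96 h limit with a window long enough for final culture results, and state the censoring rule.
- Report time to a reported negative result separately. Fungal cultures are held for up to 24 days, so a pooled figure would largely reflect laboratory holding times.
- Add time to the first postoperative antibiotic change or stop, without requiring attribution to a particular result.
- Keep time to first detection as a descriptive measure, with detection defined for each test.

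The cost is protocol wording and a few time fields. Both results are already posted to the record (Section 2.1, General Design), and antibiotic data are already abstracted (Section 5.3). The documents do not say that posting times are on the case report form, so fields may have to be added. A rule is needed for cultures reported in stages. The report should also state that an ONT result is not fully equivalent to culture: in the pilot it found 75% of cultured bacterial species and predicted 81% of observed resistance phenotypes. None of this changes patient care.

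### Time to first microbial detection is compared within 96 hours with no value assigned to patients detected later or never, so the comparison of available times is not a randomised one

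*Combined protocol and SAP*

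**What the plan says.** Section 6.2 defines the variable: "We will calculate the time from randomization to first microbial detection within a patient". It then reports the "mean difference in time to first microbial detection within 96 hours post randomization" with a 95% confidence interval. The comparison of arms "will be performed using Wilcoxon rank sum test or two sample t-test as appropriate".

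The section does not say whether a detection after 96 h is excluded, capped or censored, or how a patient with no detection is counted. The missing-data paragraph covers only lost samples and computer failure.

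Section 2.3 lists "Timeliness of sample analysis" as a secondary endpoint. On speed, 1.1 gives ONT "with a median time of 14 hours compared to 98 hours for traditional culture". Section 1.4 repeats the two numbers but calls the culture figure an average: "turnaround for ONT sequencing was just 14 hours compared to an average turnaround time of 98 hours for SC".

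**The concern.** Neither named test can use a patient who has no event time. If such patients are left out, each arm's sample is defined by the outcome being studied, and the share left out differs between arms because the two tests differ in positivity. The t-test or Wilcoxon then no longer has randomisation behind it.

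The 96 h limit adds a second problem. ONT results should almost all arrive well before it, whereas culture results may fall on either side. Whatever is done with late times therefore acts almost entirely on the control arm.

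Faster identification is the first step in the trial's hypothesis, and this is the only analysis that addresses it. In an open-label trial (4.3), a rule left unstated may be settled after the data are seen.

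**Working it through.** **Check on the detection rates.** The plan gives no sample size for time to detection, but its overall figure confirms how the 6.1 rates are meant. With 54% and 77%, two-sided 0.05, 80% power and pooled variance (mean rate 0.655):

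n = [1.960·√(2·0.655·0.345) + 0.842·√(0.54·0.46 + 0.77·0.23)]² / 0.23² = (1.318 + 0.549)² / 0.0529 ≈ 65.9, so 66 per group, as stated.

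**Patients with a detection time, 70 per arm.**
- Control: 70 × 0.54 = 37.8 with a time, 46% without.
- ONT: 70 × 0.77 = 53.9 with a time, 23% without.

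These are rates per test. Arm 2 also has culture, so its undetected share could be below 23% if culture counts there. This first result does not depend on the speed of culture.

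**Effect of the 96 h limit among detected patients.** The documents give no mean time to first detection by culture and no standard deviation, so these inputs are assumptions:
- ONT: lognormal, median 14 h, log-SD 0.3, hence mean 14·exp(0.045) = 14.6 h.
- Control: lognormal, mean m of 48, 72 or 98 h, log-SD σ from 0.3 to 0.7. Section 1.1 says culture results usually arrive over 2–4 days, and 1.4 gives a 98 h average turnaround.

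With μ = ln m − σ²/2:
- share within 96 h: p = Φ((ln 96 − μ)/σ)
- partial mean: E = m·Φ((ln 96 − μ − σ²)/σ)
- control mean if late times are dropped: E/p
- control mean if late times are capped: E + 96(1 − p)

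Example, m = 98 and σ = 0.5: μ = 4.460, p = Φ(0.209) = 0.583, E = 98·Φ(−0.291) = 37.8.
- All detections: 98 − 14.6 = 83.4 h.
- Dropped: 37.8/0.583 − 14.6 = 50.2 h.
- Capped: 37.8 + 96·0.417 − 14.6 = 63.2 h.
- All randomised patients, with those undetected by 96 h set to 96: (0.54·77.8 + 0.46·96) − (0.77·14.6 + 0.23·96) = 86.2 − 33.4 = 52.8 h.

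Ranges over σ from 0.3 to 0.7:

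| Control mean | Late | Difference, all detections | Late dropped | Late capped | All randomised, to 96 h |
|---|---|---|---|---|---|
| 48 h | 0.7–9.0% | 33.4 h | 24.3–32.9 h | 29.5–33.3 h | 34.6–36.7 h |
| 72 h | 13.4–22.3% | 57.4 h | 34.0–51.1 h | 44.5–55.1 h | 42.8–48.5 h |
| 98 h | 37.4–46.8% | 83.4 h | 40.5–61.5 h | 55.8–70.8 h | 48.8–56.9 h |

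At a control mean of 98 h, dropping late times leaves about 20 to 24 of 70 control patients (37.8 × p) against about 54 of 70 ONT patients.

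**A longer horizon.** Suppose the restricted mean ran to the 24 days (576 h) that 1.1 allows for fungal culture. Undetected patients alone would contribute (0.46 − 0.23) × 576 = 132 h to the difference. The total would be (0.54·48 + 0.46·576) − (0.77·14.6 + 0.23·576) ≈ 147 h at a control mean of 48 h, and about 174 h at 98 h. The differences in speed among detected patients are 33 h and 83 h.

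**The case against.** The strongest objection is that the text does not say late results are thrown away. A difference in time within 96 h can equally be read as a mean restricted to 96 h, with later times capped. If undetected patients were also set to 96 h, every randomised patient would be included and the comparison would be sound. That stands as a possible reading, but the plan does not state it, and the readings give different answers.

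A reader might infer that, because culture takes 98 h, about half of control detections fall outside the limit. The documents do not support this:
- The 98 h is turnaround to a result, and 1.1 ties its roughly four days to final bacterial results. The 1.4 statement "On average, it took 4.8 days" concerns completed identification. The endpoint is first detection.
- Supplement S2 has aerobic plates read after as little as 16 h of incubation. Section 1.5.1, on the other hand, puts receipt of results at 4–7 days, so the documents are mixed.
- Reading 98 h as a median gives 51–53% late at log-SD 0.3–0.7. It also implies a mean of 98·exp(σ²/2) = 103–125 h, above the 98 h average in 1.4.

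A reader might also infer that the ONT advantage is understated overall. That is shown only among detected patients. With all randomised patients followed to 96 h and a control mean of 48 h, the difference is 35–37 h against 33 h, because it absorbs the gap in positivity.

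Finally, timeliness is secondary in 2.3 and absent from the secondary endpoints in 5.3. Neither the primary endpoint nor the sample size is affected, and ONT remains faster in every scenario above.

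**Conclusion.** The concern holds as a gap in the definition of a listed secondary endpoint. The plan gives no value to late or absent detections and names tests that need one. At the 6.1 rates, a comparison of available times leaves out about 46% of one arm and 23% of the other and is not a randomised comparison. This rests only on the plan's own rates.

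Among detected patients, dropping or capping late times understates the speed advantage. The size depends on assumed lognormal times: large if control first detection averages near 98 h (83 h becomes 41–62 h dropped or 56–71 h capped), small if it averages 48 h (33 h becomes 24–33 h dropped). The documents do not establish which case applies, that late results will be discarded, or the direction of bias over all randomised patients. The point should be corrected, but it does not threaten the trial's main result.

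**What to change.** Amend 6.2 as follows.

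1. Define first detection in each arm. For Arm 2, state whether it is the earlier of culture and ONT or ONT alone. State whether first growth, a first reported organism or completed identification counts.
2. Analyse all randomised patients. Report cumulative incidence of first detection by arm, keeping patients with no organism as undetected.
3. Compare arms with a log-rank-type test, or a Wilcoxon test that gives patients undetected by 96 h the worst rank.
4. Report the difference in restricted mean time to 96 h in all randomised patients, stating that it reflects both speed and positivity.
5. Give time among detected patients, including detections after 96 h, as descriptive only.

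Do not use a 24-day restricted mean as the measure of speed. It would mostly measure the positivity gap, which 6.2 already compares as a proportion.

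The cost is a change of wording, a summary less simple than a mean difference, and some abstraction. Section 5.3 captures all culture and ONT results but does not list the time of first detection, which must be recorded with each result.
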